Pilocarpine, a parasympathomimetic agent, is a glaucoma medication that works by causing contraction of the ciliary muscle leading to opening of the trabecular meshwork[3]. Due to its frequent dosing requirement and large number of ocular and systemic side effects, pilocarpine has largely fallen out of favor for the treatment of primary open angle glaucoma (POAG), except in patients for whom few other alternatives exist. However, pilocarpine is often used after trabectome surgery. The rational for its use after Trabectome procedure is for its miotic effect, which theoretically may prevent the formation of peripheral anterior synechiae. Formation of peripheral anterior synechiae can lead to the closure of the cleft that is generated and the possibility of failure of the procedure. While the theoretical benefit of pilocarpine has been proposed, its actual benefit has never been proven. In this study, we aim to evaluate whether Trabecome / Cataract surgery without pilocarpine is non-inferior to Trabecome / Cataract surgery procedure followed by treatment with pilocarpine. The outcomes to be evaluated are the degree (percentage) of IOP lowering from baseline after the procedure, the mean post-operative IOP, the number of IOP lowering agents required to achieve goal IOP, and the rate of progression towards further glaucoma surgeries.

Key Questions

1. What are the demographics and characteristics of patients undergoing combined cataract/trabectome surgery at Montefiore Medical Center?
2. What is the post procedure percent IOP drop at 1 month, 6 months and 1 year after surgery.

3. What is the number of pre and post procedure drops required to achieve goal IOP at 6 months, 1, 2 and 3 years after combined cataract/trabectome surgery in patients treated with post-op pilocarpine vs control?
4. What is the rate of progression towards further surgery in patients treated with post-op pilocarpine vs control over a 3 year follow up period?
5. What is the rate of pilocarpine related side effects and drug discontinuation due to adverse effects?

Objectives

1. To determine whether Trabectome/cataract surgery without pilocarpine is non-inferior to Trabecome / Cataract surgery procedure followed by treatment with pilocarpine in decreasing IOP at 1 year after surgery.
2. To determine the incidence and characteristics of pilocarpine induced side effects in this population.

Selection of Patients

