1. Inclusion Criteria: Patients with ocular hypertension or open angle glaucoma undergoing combined cataract surgery with trabectome in a single surgical center at Montefiore Medical Center with a single provider between March 1st 2018 and July 1st 2020
2. Exclusion Criteria: Patients with previous history of eye surgeries (including laser procedures).
3. Age Range: 30 to 100 years old

Study Design

Prospective randomized controlled trial

Study Methods

140 consecutive patients with POAG who are planned for combined cataract/trabectome surgeries will be consented for inclusion in this study. Patients will be randomized to one of two study arms, using an online computer randomizer; the first group labeled “treatment group” and the second “control group.” The treatment group will receive post-operative treatment with pilocarpine 2% for 1 month postoperatively, in addition to the standard post-operative surgical drops including topical steroids and topical antibiotic drops. The control group will receive the usual post-operative drop schedule without pilocarpine. Most surgeons who do combined trabectome/cataract surgery will include the use of pilocarpine besides steroid and antibiotic. However, it is also acceptable for patients to only receive steroid and antibiotics (without pilocarpine) after such surgery. Patients in both groups will be followed for 1 year with the primary endpoint of percent decrease in IOP after surgery at 1 year. Secondary outcome measures will include: progression of glaucoma on OCT and HVF testing, medication side effects, number of pre and postoperative drops the patient was using before and after surgery, and need for further glaucoma surgery. All subsequent visits will be according to routine post-operative monitoring, where visual acuities, intraocular pressures, gonioscopy measurements will be performed at the slit lamp. These visits will coincide with standard of care post op follow up visits.

Participant recruitment

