140 consecutive patients with POAG who are planned for combined cataract/trabectome surgeries with the principal investigator will be consented for inclusion in this study. Patients will be given a copy of the consent document to read over and they will be given time to ask any questions they have about the study. Participation in the study is completely voluntary and if they do not wish to participate in the study they can continue their care with the principal investigator and undergo their combined cataract/trabectome surgery without any remediation and their information will not be used in the study.

Confidentiality of data

Electronic data will be saved under a password protected computer in an anonymized fashion. Only the co-investigators will have access to the data for the duration of the study and only the co-investigators will be able to add data to the database. The data will be destroyed at the completion of the study.

Consent

Patients will provide written consent prior to participation in the study, as obtained by the investigators of this study. Once eligible patients are identified for the procedure at the pre-op visit, they will be asked to fill out the informed consent form and all questions will be answered. Patients will be informed of all risks and benefits of both the procedure and the use of pilocarpine as outlined further below. As no placebo will be utilized, patients will not be blinded to which group they are in.

Risks and Benefits:

1. Risks: Potential risks include the proposed risk of failure of the trabectome surgery secondary to scarring in both groups. Additional risk includes side effects of the use of pilocarpine, including but not limiting to: blurry vision, decrease night vision, headaches, browache, nausea, vomiting, diarrhea.
2. Benefits: Patients - the benefit to not using pilocarpine is a decrease in the medication burden and a decrease in the potential side effects that can occur with pilocarpine use. Additional benefits include for society and for the investigators due to the knowledge that will be gained from the study.

Statistical Considerations

1. Proposed sample size: 140
2. Proposed time period to be evaluated: 1 year of follow up

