3. Feasibility of study – Over the time period 2/2016 – 9/2017, [name] completed 118 combined cataract/trabectome surgeries. Based on her historical usage and her usage of the combined procedure only increasing due to its success, we believe 140 patients can be recruited over a 1.5 – 2 year time frame.

Analytic Plan

All analyses will be based on the intent-to-treat approach (ITT). Standard descriptive statistics will be used to summarize the baseline characteristics and outcomes of the two treatment arms. The primary endpoint, percent decrease in IOP at 1 year after surgery compared to baseline, will be analyzed by computing the mean difference of this endpoint between treatment groups (pilocarpine - no pilocarpine) along with the corresponding two-sided 95% confidence interval. Non-inferiority of treatment without pilocarpine will be declared if the upper limit of the two-sided confidence interval is less than the margin of non-inferiority, which is deemed to be 5% in this study. Since the ITT approach can be anti-conservative in non-inferiority trials, a per-protocol analysis will also be performed. Two sample tests of the standard null hypothesis of no difference between groups will be conducted using the student T-test

for continuous variables or chi-square test for categorical variables (e.g., occurrence of side effects, need for further surgery). Linear or logistic regression models will be fit to the data to adjust for any baseline characteristics which are found to differ between treatment arms. In addition, generalized linear mixed models will be fit to the repeated measures obtained post-surgery, as part of every standard clinic encounter during follow-up, to assess whether the longitudinal trends in the outcomes differ between groups.

Sample size considerations

The sample size for this study is 140 subjects (70 per group). This sample size will yield greater than 95% power at a 1-sided Type I error rate of 2.5% (two-sided of 5%) to declare non-inferiority of the no pilocarpine group to the pilocarpine group with respect to the percent decrease in IOP after surgery, assuming an alternative hypothesis of no difference between groups, a non-inferiority margin of 5%, and a SD of 7.5% in both groups based on prior studies.

Data and Safety Monitoring Policy

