As pilocarpine is an FDA approved medication with the overall risk level to the patient deemed to be mild, DSM will be undertaken by the investigator. At each office visit over the course of the life of the study (all visits as part of standard of care) specific attention will be made to reviewing whether the patient is having any potential side effects of the medication. If any side effects are noted and either the side effect cannot be tolerated by the patient or it is deemed to not be safe for the patient to continue to use the medication, the medication will be stopped and the patients inclusion in the study terminated.

1. Hu, K., et al., *Ab interno trabecular bypass surgery with Trabectome for open angle glaucoma*. Cochrane Database Syst Rev, 2016(8): p. Cd011693.
2. Mizoguchi, T., et al., *Clinical results of Trabectome surgery for open-angle glaucoma*. Clin Ophthalmol, 2015. 9: p. 1889-94.
3. *Isotox Carpine (pilocarpine)[Package insert]*: Alcon, Inc. TX. 2010

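### Need for further glaucoma surgery is compared by a chi-square that ignores follow-up time, with no rule for incomplete follow-up, although one arm has its own route to early exit

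*Combined protocol and SAP*

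**What the plan says.** Study Methods lists the outcome as secondary ("and need for further glaucoma surgery") and gives it no time window. The Analytic Plan assigns it a "chi-square test for categorical variables (e.g., occurrence of side effects, need for further surgery". The only adjusted model there that suits a yes/no outcome is logistic regression. The mixed models are for repeated clinic measures. The document contains no time-to-event method, censoring rule or rule for missing outcomes.

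The period is stated in two ways. Key Question 4 asks: "What is the rate of progression towards further surgery in patients treated with post-op pilocarpine vs control over a 3 year follow up period". Study Methods says "Patients in both groups will be followed for 1 year", and Statistical Considerations says "Proposed time period to be evaluated: 1 year of follow up".

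Two passages bear on how complete follow-up will be. Study Methods ties observation to routine care: "These visits will coincide with standard of care post op follow up visits". The Data and Safety Monitoring Policy says that, for side effects that cannot be tolerated or are judged unsafe, "the medication will be stopped and the patients inclusion in the study terminated". Against this, the Analytic Plan states "All analyses will be based on the intent-to-treat approach (ITT"), and adds a per-protocol analysis because of the non-inferiority aim.

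**The concern.** A chi-square on a yes/no outcome compares like with like when every patient is observed for the same period, or when the plan says what happens to those who are not. Neither is secured here. The termination rule depends on pilocarpine side effects, and only one arm is assigned pilocarpine. Because that treatment lasts 1 month, such exits would come early and leave most of the year unobserved in that arm alone.

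The handling of these patients could therefore create a difference between arms where none exists. If a missing surgery record is read as no surgery, the error favours pilocarpine. That bears on the trial's question, which is whether pilocarpine can be left out.

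**Working it through.** **The plan's own figure.** The documents give no surgery rate, dropout rate or power for this outcome. The only power figure is for the primary endpoint. With 70 per group, margin 5 and SD 7.5, the standard error is 7.5 × √(2/70) = 1.268. Then 5/1.268 − 1.96 = 1.98, which gives power of 97.6% (97.5% by noncentral t). This agrees with the stated figure of more than 95% and is not affected by this point.

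**Inputs.** From the documents: 70 per arm, 1 year of follow-up, pilocarpine for 1 month. Assumed, because the documents give none: true 1-year surgery risk p = 15% in both arms with a constant hazard; 10% of each arm lost at times spread uniformly over the year; and a share d of the pilocarpine arm leaving at month 1, unrelated to surgery risk.

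**If leavers are scored as no surgery:**
- Yearly hazard: −ln(0.85) = 0.1625.
- Chance that surgery is seen in a patient lost at a uniform time: 1 − 0.15/0.1625 = 7.7%.
- Chance that surgery is seen by month 1: 1 − 0.85^(1/12) = 1.35%.
- Control, observed: 0.90 × 15% + 0.10 × 7.7% = 14.3%.
- Pilocarpine, observed: (1 − d) × 14.27% + d × 1.35%.

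| d | Pilocarpine | Control | False difference | Patients (of 70) | 95% CI half-width |
|---|---|---|---|---|---|
| 5% | 13.6% | 14.3% | 0.6 points | 0.5 | 11.5 points |
| 15% | 12.3% | 14.3% | 1.9 points | 1.4 | 11.2 points |
| 25% | 11.0% | 14.3% | 3.2 points | 2.3 | 11.0 points |

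The half-width is 1.96 × √[(p₁(1 − p₁) + p₀(1 − p₀))/70]. A simulation of 4,000 trials per scenario gave 12.4% v 14.2% at d = 15% and 11.1% v 14.3% at d = 25%. Kaplan-Meier gave 15.1% v 15.0% in both.

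**Effect on the test.** A second set of simulations (5,000 per scenario, no true difference, no loss other than month-1 exits from the pilocarpine arm) gave these two-sided rejection rates for the chi-square with leavers scored as no surgery:
- 10% risk, 10% exit, 12 months: 5.3%
- 20% risk, 20% exit, 12 months: 8.2%
- 20% risk, 30% exit, 12 months: 12.8%
- 30% risk, 30% exit, 36 months: 22.1%

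At 5% exit the normal approximation gives 5.0% to 5.4% over risks of 5% to 30%. Over the scenarios with exits, the log-rank test with leavers censored stayed between 4.5% and 5.3%.

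**If leavers are excluded.** The same simulations gave 4.4% to 5.5% for the chi-square, so its level holds when leaving is unrelated to surgery risk. When it is related, let leavers have risk y and the whole arm risk p. Those who stay then have risk p − [d/(1 − d)] × (y − p). At d = 15% the multiplier is 0.15/0.85 = 0.18, so every 10 points by which leavers' risk exceeds the arm average lowers the pilocarpine estimate by 1.8 points.

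**With complete follow-up** the two tests behave alike: 5.5% for the chi-square and 5.4% for the log-rank.

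**The case against.** A reader might infer that the plan counts early leavers as surgery-free because it is analysed by ITT. The documents do not say so. ITT fixes the arm in which a patient is analysed; it does not fill in a missing outcome. Leavers could be scored as no surgery, excluded, or still followed for surgery, and the plan is silent. What remains is that excluding them departs from the ITT statement and following them sits uneasily with the termination rule, so the choice has to be written down.

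A reader might also infer that the chi-square is wrong in itself, or that the word rate in Key Question 4 commits the trial to a time-to-event analysis. Neither follows. A proportion at a common 1-year point is an accepted summary when follow-up is complete, and Key Question 5 uses the same word for side effects, where a proportion is a natural reading. Routine-care visits apply to both arms and do not by themselves show unequal follow-up.

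The size is also fairly disputed. All rates are assumed, the policy describes the overall risk to patients as mild, and a bias of 2 to 3 points is small beside a confidence interval of about ±11 points. Finally, the simulations make leaving independent of surgery risk, which favours Kaplan-Meier by construction. For patients who leave at month 1, Kaplan-Meier adds only one month of information to simple exclusion, and it shares the same weakness if leaving is informative. These points stand and limit the claim.

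**Conclusion.** The point holds as a gap in a secondary analysis that is cheap to close. The named test ignores follow-up time, no rule covers incomplete follow-up, and the protocol contains an early exit route that can operate only in the pilocarpine arm. The bias arises if leavers are scored as no surgery. It then favours pilocarpine, by about 2 points at 15% arm-specific exit and about 3 points at 25%, and is negligible at about 5%. These sizes rest on an assumed 15% true risk, 10% random loss, a constant hazard and exits at month 1. If leavers are excluded, there is no such bias provided that leaving is unrelated to surgery risk, but the analysis is no longer ITT. The primary non-inferiority test and the sample size are unaffected.

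**What to change.** 1. Replace the chi-square for this outcome with time from the combined operation to first further glaucoma surgery, censored at last contact or at the end of the stated window. Report Kaplan-Meier risk by arm, the difference (no pilocarpine minus pilocarpine) with a 95% CI from Greenwood variances, and a log-rank test. Use Cox rather than logistic regression for an adjusted estimate.
2. State one window for the outcome by reconciling the 3 years of Key Question 4 with the 1 year in Study Methods and Statistical Considerations.
3. Reconcile the termination of inclusion in the Data and Safety Monitoring Policy with the ITT statement, so that surgery outcomes are recorded for all randomised patients where consent allows. This protects against informative exit in a way that a change of test cannot.
4. Add a sensitivity analysis for censoring, since exits for side effects may not be non-informative as Kaplan-Meier and log-rank assume.

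The cost is SAP wording, two dates per patient (further surgery and last contact), and any continued outcome recording under item 3. The documents do not list the data fields, so whether both dates are already captured should be confirmed. Little is lost if follow-up proves complete, because the two tests then behave alike.

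### The non-inferiority test ignores baseline IOP, and covariates are picked by observed imbalance; a pre-specified ANCOVA on baseline IOP would add precision, if baseline IOP is prognostic, with no extra data.

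*Combined protocol and SAP*

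**What the plan says.** The Analytic Plan defines the endpoint and the decision rule in consecutive sentences:

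- The endpoint is "The primary endpoint, percent decrease in IOP at 1 year after surgery compared to baseline".
- The analysis consists of "computing the mean difference of this endpoint between treatment groups (pilocarpine - no pilocarpine) along with the corresponding two-sided 95% confidence interval".
- The decision is then read from that interval: "Non-inferiority of treatment without pilocarpine will be declared if the upper limit of the two-sided confidence interval is less than the margin of non-inferiority", and the margin is 5%.
- A second analysis population is added: "Since the ITT approach can be anti-conservative in non-inferiority trials, a per-protocol analysis will also be performed". The plan does not say whether that analysis is adjusted.

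No covariate appears in any of this. Adjustment comes later, after the t-tests and chi-square tests: "Linear or logistic regression models will be fit to the data" in order to "adjust for any baseline characteristics which are found to differ between treatment arms". The plan does not say how a difference between arms is judged or which characteristics are candidates. The generalised linear mixed models that follow are additional and address longitudinal trends, so they do not supply an adjusted 1-year comparison.

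Sample size considerations sets 70 per group and claims power above 95%, "assuming an alternative hypothesis of no difference between groups, a non-inferiority margin of 5%, and a SD of 7.5% in both groups".

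**The concern.** In a randomised trial, baseline differences between arms arise by chance. What a covariate adds to precision depends on how well it predicts the outcome, not on how unevenly it happened to fall. A rule that selects on imbalance can omit a strong predictor that is balanced and admit a useless one that is not.

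Baseline IOP is the obvious candidate. It is the denominator of the endpoint, so some correlation with it is plausible, and it must be recorded for every patient analysed. Study Methods describes an online randomiser and mentions no stratification by baseline IOP. Under the present text, whether baseline IOP enters a model depends on the data and on a criterion that is not written down. Two analysts following the plan could fit different adjusted models.

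At stake are the width of the interval that is compared with the 5-point margin, and whether the adjusted analysis can be reproduced from the plan.

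**Working it through.** **Inputs.** From the documents: 70 per arm, SD 7.5, margin 5, true difference 0, one-sided alpha 2.5%. Assumed, because the documents give no value: r, the within-arm correlation of baseline IOP with percent decrease; an alternative SD of 10; and three possible meanings of a difference between arms.

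**1. The plan's own figure.** SE = 7.5 × √(2/70) = 1.268. Power = Φ(5/1.268 − 1.96) = Φ(1.984) = 97.6%. The noncentral t with 138 df gives 97.5%. The claim of more than 95% is reproduced.

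**2. Effect of ANCOVA.** Adjustment multiplies the SE by √(1 − r²), so power = Φ(5/(SE × √(1 − r²)) − 1.96). At SD 10 the unadjusted SE is 1.690. Half-widths are means over 100,000 simulated trials; the unadjusted value is 2.50.

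| \|r\| | √(1 − r²) | ANCOVA half-width, SD 7.5 | Power, SD 7.5 | Power, SD 10 |
|---|---|---|---|---|
| 0 | 1.00 | 2.51 | 97.6% | 84.1% |
| 0.3 | 0.95 | 2.40 | 98.5% | 87.3% |
| 0.5 | 0.87 | 2.17 | 99.5% | 92.7% |
| 0.7 | 0.71 | 1.79 | 99.98% | 98.5% |

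The r = 0 powers equal the unadjusted ones, apart from the one degree of freedom.

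**3. Does the planned SD pin down r?** No. A grid with assumed mean IOP of 20 at baseline and 15 at 1 year, SDs of 1 to 5 at each time, and correlations between the two IOPs of 0 to 0.95 gave 36 combinations with an endpoint SD of 7.2 to 7.8. Among them r ran from −0.85 to 0.95, with median 0.39.

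**4. How often would the imbalance rule admit baseline IOP?** For a standardised-difference cut-off c, the probability is 2 × (1 − Φ(c/√(2/70))): 55.4% at c = 0.1 and 23.7% at c = 0.2. With p < 0.05 as the criterion it is 5%.

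**5. If the adjusted result replaced the raw one whenever baseline IOP was admitted.** The plan does not say that it would. Simulation: 100,000 trials per cell, bivariate normal, r = 0.5.

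| Rule | Power, SD 7.5 | Power, SD 10 | One-sided type I error (true difference 5, SD 7.5) |
|---|---|---|---|
| Unadjusted | 97.5% | 83.5% | 2.4% |
| Adjust if p < 0.05 | 97.9% | 84.6% | 2.1% |
| Adjust if standardised difference > 0.2 | 98.6% | 87.1% | 1.8% |
| Adjust if standardised difference > 0.1 | 99.1% | 89.7% | 1.9% |
| ANCOVA always | 99.5% | 92.3% | 2.4% |

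The imbalance rule does not inflate type I error. It recovers only part of the available precision.

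**6. Check on the real percent-decrease scale.** The calculations above assume normality, and a ratio endpoint need not be normal. Simulating IOP directly, with the assumed means of 20 and 15:

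| Baseline SD / 1-year SD / correlation | Half-width, unadjusted → ANCOVA | ANCOVA type I error |
|---|---|---|
| 3 / 3 / 0.9 | 2.41 → 2.28 | 2.5% |
| 2 / 2 / 0.65 | 2.60 → 2.58 | 2.5% |
| 2 / 1.5 / 0.5 | 2.56 → 2.22 | 2.4% |
| 2 / 1 / 0.4 | 2.46 → 1.58 | 2.6% |
| 1 / 2 / 0.8 | 2.47 → 2.02 | 2.5% |

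ANCOVA holds its type I error close to 2.5%. The gain ranges from almost nothing to about a third of the width.

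**The case against.** The case against giving this much weight is substantial.

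- **The primary rule contains no error.** Estimator, interval, margin and decision are all fixed in the text. That stands: this is a better method, not the repair of an invalid one.
- **The power gain is small on the plan's own figures.** It cannot exceed 100 − 97.6 = 2.4 points, and the half-width of 2.50 is already half the margin. At the grid median of r = 0.39, power would be 99.0%, a gain of 1.4 points. This stands too.
- **Larger gains need an SD above 7.5 together with a sizeable r, and the two are linked.** Both follow from the same IOP distributions. With means of 20 and 15, baseline SD, 1-year SD and correlation of 4, 4 and 0.8 give an endpoint SD of about 13 with r near −0.09, so almost no gain. Inputs of 4, 3 and 0.5 give r of about 0.52. A larger SD therefore does not guarantee a benefit, and the SD 10 column above is conditional on r.
- **The natural reading is that the regressions are supplementary.** The non-inferiority rule is tied to the raw difference, so the threshold results in step 5 show what could happen, not what the plan prescribes. The per-protocol analysis is likewise most naturally read as the same unadjusted comparison in another population. Both points are fair, and the conclusion relies on neither.

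None of this is a reason to leave baseline IOP out. If it is not prognostic, adjusting costs about 0.01 points of half-width. The data-dependent covariate choice also remains whatever the values of SD and r.

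**Conclusion.** The concern holds. The non-inferiority decision uses an unadjusted difference, the adjusted models take covariates by observed imbalance on an unstated criterion, and baseline IOP is pre-specified nowhere. The unadjusted test is valid and the stated power is correct.

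The benefit of ANCOVA rests wholly on r, which is unknown. For assumed |r| of 0.3 to 0.7 the interval narrows by about 5% to 29%; at r = 0 there is no gain. The effect on power is minor if the SD is 7.5. Unadjusted power falls below 95% once the SD exceeds about 8.2, and adjustment is then worth more if baseline IOP is prognostic. These figures concern the primary endpoint only. For the logistic models the point is pre-specification alone. The change is worth making because it is nearly free, not because the present primary analysis would mislead.

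**What to change.** 1. Make the primary analysis an ANCOVA of 1-year percent decrease on arm and baseline IOP. Compare the upper limit of the two-sided 95% confidence interval for the adjusted difference (pilocarpine minus no pilocarpine) with the 5-point margin.
2. State that the per-protocol analysis uses the same model.
3. Keep the unadjusted difference as a sensitivity analysis.
4. Drop selection by observed imbalance, and list the covariates of the linear and logistic models in advance, chosen for expected prognostic value.

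The cost is SAP wording and one degree of freedom: the half-width goes from 2.50 to 2.51 points if r = 0. No data are added, the margin stays on the same scale, and the sample size and clinical procedures do not change.

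### Side effects are tested between arms, but the only ascertainment described is an unmasked review for effects of a drug that controls do not take; no common, attribution-free symptom record is specified

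*Combined protocol and SAP*

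**What the plan says.** - **Ascertainment.** The Data and Safety Monitoring Policy gives the only instruction on how side effects are found: "specific attention will be made to reviewing whether the patient is having any potential side effects of the medication". It applies to the patient at every office visit throughout the study. The paragraph opens with these words, which go on to name the investigator: "As pilocarpine is an FDA approved medication with the overall risk level to the patient deemed to be mild, DSM will be undertaken by the". Its consequence is that the medication is stopped. In that paragraph the medication is therefore pilocarpine.
- **Exposure.** Study Methods: "The control group will receive the usual post-operative drop schedule without pilocarpine". The pilocarpine course lasts 1 month. Both arms receive steroid and antibiotic drops and are followed for 1 year.
- **Blinding.** Consent: "As no placebo will be utilized, patients will not be blinded to which group they are in". No masked assessor is described.
- **Outcome and test.** Study Methods: "Secondary outcome measures will include: progression of glaucoma on OCT and HVF testing, medication side effects". The Analytic Plan assigns the between-group test: "chi-square test for categorical variables (e.g., occurrence of side effects, need for further surgery".
- **Objective 2.** "To determine the incidence and characteristics of pilocarpine induced side effects in this population". Key Question 5 asks for the rate of pilocarpine-related side effects and of discontinuation because of them.
- **Symptoms.** Risks and Benefits lists, as a non-exhaustive set, "blurry vision, decrease night vision, headaches, browache, nausea, vomiting, diarrhea".

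The documents contain no symptom checklist, no definition of a side effect that applies to both arms, and no statement on whether controls are asked the same questions.

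**The concern.** A between-arm test of occurrence needs an event that can be recorded in the same way in both arms. The plan describes a review directed at one drug, carried out by people who are not said to be masked, in patients who know whether they received it.

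Most of the listed symptoms are non-specific. Both arms have just had cataract and Trabectome surgery and are using other drops, so some background rate of blurred vision, headache or nausea among controls is plausible. Whether it is counted depends on whether, and how, controls are asked.

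At stake is the side-effect comparison. Risks and Benefits gives fewer side effects as a benefit to patients of omitting pilocarpine. An excess produced by uneven recording would lend that statement support it had not earned. Symptoms that were never asked about cannot be recovered at analysis.

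**Working it through.** **The plan's own figure.** The only computed figure in the documents is power for the primary endpoint. With 70 per arm, margin 5, SD 7.5 and one-sided 2.5%, the standard error is 7.5 × √(2/70) = 1.268. Then 5/1.268 − 1.960 = 1.984, giving power of 97.6% (97.5% with the t distribution). This agrees with the stated value of more than 95%. The present point does not depend on it.

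**Two readings of the side-effect outcome.**

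*Reading 1: only effects attributed to pilocarpine count.* Controls take none, so their count is zero or nearly so by definition. With Pearson's statistic X² = d² / [2p̄(1 − p̄)/n], 4 of 70 against 0 of 70 gives d = 4/70 = 0.0571 and p̄ = 4/140 = 0.0286, so X² = 0.003265/0.000793 = 4.12, above the 5% critical value of 3.84. Four attributed events would give a significant uncorrected result whatever the background symptom rate. The test then tells the reader nothing about excess over control.

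*Reading 2: symptoms count, whatever their cause.* Let p₁ and p₀ be the true symptom proportions on pilocarpine and control, with full capture on pilocarpine and a fraction c captured in controls. The expected observed difference is p₁ − c·p₀, so the bias is (1 − c)·p₀. This bias does not depend on whether pilocarpine has a true effect.

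**Illustration under Reading 2.** Inputs from the documents: 70 per arm and a chi-square test (Analytic Plan, Sample size considerations). Inputs assumed, and not in the documents: p₀ of 10%, 20% and 30%; c of 100%, 70% and 50%; full capture on pilocarpine; a two-sided 5% level for this test; and no true difference (p₁ = p₀ = p).

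The rejection probability is Σ Bin(x₁; 70, p) × Bin(x₀; 70, c·p), summed over all pairs (x₁, x₀) with |x₁ − x₀|/70 > 1.96 × √[2p̄(1 − p̄)/70], where p̄ = (x₁ + x₀)/140. The continuity-corrected version first subtracts 1/70 from the absolute difference.

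| True rate, both arms | Control capture | Spurious excess (1 − c)·p | Rejects, uncorrected | Rejects, corrected |
|---|---|---|---|---|
| 10% | 100% | 0 points | 5.1% | 2.5% |
| 20% | 100% | 0 points | 5.1% | 2.9% |
| 30% | 100% | 0 points | 5.2% | 3.2% |
| 10% | 70% | 3 points | 9.9% | 5.1% |
| 20% | 70% | 6 points | 15.6% | 10.5% |
| 30% | 70% | 9 points | 23.4% | 17.2% |
| 10% | 50% | 5 points | 20.4% | 11.4% |
| 20% | 50% | 10 points | 38.2% | 29.7% |
| 30% | 50% | 15 points | 57.7% | 48.5% |

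With equal capture the uncorrected test holds its level. With unequal capture, nearly all rejections point towards more side effects on pilocarpine.

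**The case against.** **A reader might infer that controls will not be questioned. The documents do not say so.** The review is of the patient, at every office visit, with no restriction to one arm. It continues throughout the study while pilocarpine lasts 1 month, so it cannot be confined to patients currently on the drug. This stands: unequal questioning is an unaddressed risk and not a stated procedure. What remains is that, even if all patients are reviewed, a control is being reviewed for effects of a drug not taken, with no common questions.

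**The quoted sentence is a safety rule, not an outcome definition.** In Study Methods, medication side effects could include those of the steroid and antibiotic drops. That is a fair reading, but no other definition or method of ascertainment is given, so the ambiguity stays.

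**A reader might infer that Objective 2 cannot be answered.** As worded, it and Key Question 5 can be met by describing attributed effects and discontinuations in the treated arm. Under-asking controls does not change that count. This stands. The weakness is in the between-arm test.

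**The magnitudes are assumed, and the null case is unfavourable to the plan.** The rates and capture fractions are not in the documents, full capture on pilocarpine is an upper limit, and a continuity correction lowers the figures. The Background also expects pilocarpine to have side effects, so inflation of a real difference is likelier than a difference from nothing. All of this stands as a limit on the error rates. The bias of (1 − c)·p₀ applies with or without a true effect.

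**Conclusion.** The point holds as a gap in specification. The plan tests side effects between arms without a measure that can be read the same way in both. On one reading the control rate is near zero by construction and the test is uninformative; on the other, knowledge of the arm can inflate the excess.

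Under the stated assumptions the uncorrected test falsely rejects about 10% to 58% of the time, and about 5% to 49% with a continuity correction, with a spurious excess of 3 to 15 percentage points. These figures show sensitivity. They do not predict this trial, because the documents give neither symptom rates nor capture fractions.

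The scope is a secondary outcome and its between-arm comparison. The primary IOP analysis, the margin, the sample size and a within-arm description under Objective 2 are not affected. The change is worth making because it is cheap and because missing symptom data cannot be repaired later.

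**What to change.** 1. **Collection.** At each existing visit in the first post-operative month, ask every patient in both arms the same checklist: the symptoms listed under Risks and Benefits plus an open item for anything else. Record the answers regardless of presumed cause, and before the drop list is reviewed. Keep the every-visit safety review in the Data and Safety Monitoring Policy as it is.
2. **Between-arm analysis.** State in the Analytic Plan that the side-effect comparison uses these checklist symptoms, and report the difference in proportions with a 95% CI alongside the test.
3. **Within-arm description.** Report pilocarpine-attributed effects and discontinuations in the treated arm only, without a between-arm test.
4. **Limitation.** State that patients know their arm, so a common checklist makes the questions equal but not the willingness to report symptoms.

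Cost: a one-page form and an estimated minute or so per visit (a judgement, not a figure from the documents). No new visits are needed, and there is no change to treatment or sample size.
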